5.1 Inclusion Criteria

Registry Study: In order to be eligible to participate in the registry study, an individual must meet all of the following criteria:

- 1. Age ≥18 years of age
- 2. Hospitalized at one of the participating NYULH locations
- 3. Confirmed COVID-19 infection

Interventional Study: In order to be eligible to participate in the registry study, and individual must meet all of the inclusion criteria of the registry study plus the following critieria:

- 1. Hospitalized at NYU Tisch or NYU Winthrop
- 2. History of diabetes mellitus or blood glucose measurement >126 mg/dl

AND

EITHER

CONFIDENTIAL

This material is the property of the NYU School of Medicine and Langone Medical Center. Do not disclose or use except as authorized in writing by the study sponsor

3. History of hypertension and/or ischemic heart disease and/or heart failure

OR

4. Other co-morbid condition that in the opinion of the PI increases risk of heart or lung injury related to the aldose reductase pathway

5.2 Exclusion Criteria

Registry Study: An individual who meets any of the following criteria will be excluded from participation in the registry study:

- 1. Persons who have opted out of research participation at NYU
- 2. Pregnancy

Interventional study: An individual who meets any of the following criteria will be excluded from participation in the interventional study:

- 1. Persons who have opted out of research participation at NYU
- 2. Pregnancy
- 3. Women of childbearing potential
- 4. Breast-feeding women
- 5. Participation in another FDA-regulated investigational drug placebo-controlled clinical trial within previous 30 days
- 6. Hospital length of stay at time of study entry >14 days
- 7. Inability to comply with oral or nasogastric tube administration of study drug

Co-enrollment in other interventional studies in the COVID-19 population will be permitted if in the judgement of the PI and Sponsor, there is no anticipated increase in risk of exposure to AT-001 based on the known pathophysiology of COVID-19 infection and pharmacology of AT-001, and co-enrollment is permitted in the other protocol(s). Co-enrollment will be tracked at reported to the IRB and Sponsor.

5.3 Vulnerable Subjects

Critically-ill patients with COVID-19 may not have capacity to provide consent. The registry research is minimal risk without direct benefit. Waiver of consent and authorization are requested as is not feasible to obtain informed consent and HIPAA authorization from 500 subjects in order to conduct the prospective chart review for the registry component of the study. Although we will need access to the subjects' medical record for the duration of the study, an individual's PHI will be destroyed once they complete the study.

The primary treatment team, which consists of critical care physicians will determine subject capacity based on their interactions with the patient, presence of neurological complications, and use of sedative agents. These critical care physicians are qualified to assess capacity for consent as part of their clinical management of the patient. Subjects will be regularly assessed by the primary critical care team throughout the study to determine whether or not they have regained or lost the capacity to consent. If subjects who have the capacity to consent at the onset of the study lose capacity during the study, their legally authorized representative will be identified and consent sought for the subject's continued participation in the study. If subjects regain the capacity to consent during the study and decline to continue participation, state they will be asked if previously collected data can still be used. If they decline, this data will be discarded.

If the potential participant lacks capacity, the legally authorized representative (identified in accordance with NYS as the highest in priority of the following: court appointed LAR, health care proxy, spouse or domestic partner, adult son or daughter, parent, grandparent, adult grandchild who maintains regular contact with subject as to be familiar with subject's activities, health, or beliefs) will provide consent for the interventional study.

5.4 Strategies for Recruitment and Retention

Existing infection surveillance procedures identify all patients with COVID-19 admitted to the participating sites. These daily surveillance lists will be used to identify patients for the registry. Subjects potentially eligible for the interventional study will be identified by the intensivist in charge of patient care. The primary treatment team of critical care physicians will approach the patient and/or LAR regarding interest in participation in the study.

5.4.1 Use of DataCore/Epic Information for Recruitment Purposes

The study will use DataCore and EPIC for recruitment purposes. All subjects with COVID-19 infections are tracked to specific hospital floors for infection control purposes. Patients who meet entry criteria on COVID-19 positive hospital floors will be identified by electronic chart review. The primary care team will be contacted to confirm that the patient is appropriate for the study and willing to be approached for research.

5.5 Duration of Study Participation

Duration of study participation for the registry study is until hospital discharge, or up to 30 days, whichever is shorter.

Duration of study participation for the interventional study is up to 30 days after last dose of AT-001.

5.6 Total Number of Participants and Sites

Recruitment will end when approximately 500 participants are enrolled in the registry, and approximately 20 participants in the interventional study.

5.7 Participant Withdrawal or Termination

5.7.1 Reasons for Withdrawal or Termination

Participants are free to withdraw from participation in the study at any time upon request. An investigator may terminate participation in the study if:

Any clinical adverse event (AE), laboratory abnormality, or other medical condition or situation
occurs such that continued participation in the study would not be in the best interest of the
participant

CONFIDENTIAL

This material is the property of the NYU School of Medicine and Langone Medical Center. Do not disclose or use except as authorized in writing by the study sponsor

The participant meets an exclusion criterion (either newly developed or not previously recognized) that precludes further study participation

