2.4 Potential Risks & Benefits

2.4.1 Known Potential Risks

In subjects enrolled in the prospective registry, the only risk is potential breach of confidentiality.

In subjects enrolled in the interventional trial, additional risk is associated with investigational agent. In the completed first in human study (Study AT-001.1001) AT-001 was generally well tolerated with no safety issues identified. There were no SAEs considered treatment-related and no AEs causing discontinuation of study treatment. No clinically relevant changes in vital signs, ECG or clinical safety laboratory values were noted.

Potential risks of AT-001 based on non-clinical data and previous experience with other aldose reductase inhibitors include:

- Acute hypersensitivity reactions
- Hepatic toxicity, including fatal hepatic necrosis
- Renal toxicity: Nephrolithiasis (calculi and pelvic dilation suggestive of an obstructive mechanism leading to development of pyelonephritis were reported in female rats in a 6-month chronic toxicology study. These renal findings were not reproduced in dogs in a 9-month chronic toxicology study)
- Gastrointestinal events, including nausea, vomiting, diarrhea, flatulence, abdominal pain
- Ocular effects (two cases of non-adverse, reversible multifocal pinpoint corneal opacities in a 28day toxicology study in dogs, which was not reproduced in a 9- month chronic toxicology study)
- Hypotension and dizziness
- Skin rash/eczema
- Decreases in hemoglobin, erythrocyte count, and lymphocyte count
- Reduction in total protein in blood

The incidence of these side effects for short-term exposure to AT-001 in COVID-19 patients is unknown. We anticipate that patients with COVID-19 infection will receive concomitant treatments including off-label use of FDA-approved drugs, anti-viral therapy with remdesivir under expanded access or emergency use access, and treatment with hydroxychloroquine, convalescent sera, and/or IL-6 inhibitors within the context of clinical trials. Based on knowledge of the pathophysiology of COVID-19 infection and the pharmacology of AT-001, we do not anticipate that these concomitant medications will increase risk associated with AT-001. Patients with COVID-19 infection are known to be a high risk of complications including

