multisystem organ failure (liver, kidney, heart, lung, hematological system, nervous system with associated laboratory abnormalities) and septic shock (hypotension with metabolic abnormalities). We will collect daily clinical information to monitor evidence of organ dysfunction and septic shock in the electronic CRF. We will identify potential AE related to study drug based upon temporal relationship with study drug administration, AE in the above list of potential AE associated with aldose reductase inhibition, or suspicion that the magnitude and/or duration of organ dysfunction and associated laboratory abnormalities is different from that expected due to COVID-19 infection alone. If treatment related AE are identified, the study drug may be discontinued per the discretion of the PI, Sponsor, and treating physician.

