7.3.3 Final Study Visit

• Safety monitoring for 30 days after last dose of IP

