All unresolved adverse events should be followed by the investigator until the events are resolved, the subject is lost to follow-up, or the adverse event is otherwise explained. At the last scheduled visit, the investigator should instruct each subject to report any subsequent event(s) that the subject, or the subject's personal physician, believes might reasonably be related to participation in this study. The investigator should notify the study sponsor of any death or adverse event occurring at any time after a subject has discontinued or terminated study participation that may reasonably be related to this study. The sponsor should also be notified if the investigator should become aware of the development of cancer or of a congenital anomaly in a subsequently conceived offspring of a subject that has participated in this study.

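### Section 5.7.1 allows a dosed patient's study participation to be ended for an adverse event or a precluding exclusion criterion, which can cut recording of new non-serious AEs to 7 days and conflicts with the 30-day post-dose monitoring

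*Combined protocol and SAP*

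**What the plan says.** Section 5.7.1 opens with "An investigator may terminate participation in the study if" and gives two grounds. The first begins "Any clinical adverse event (AE), laboratory abnormality, or other medical condition or situation" and is limited to cases where staying in the study would not serve the participant's best interest. The second is "The participant meets an exclusion criterion (either newly developed or not previously recognized) that precludes further study participation". Both concern participation, not dosing.

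Stopping the drug alone is treated elsewhere. Section 2.4.1 says that if treatment-related AEs are found, "the study drug may be discontinued per the discretion of the PI, Sponsor, and treating physician". Nothing links that sentence to 5.7.1.

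On follow-up, 5.5 sets interventional participation at up to 30 days after the last dose. Section 7.3.3 requires "Safety monitoring for 30 days after last dose of IP", and 7.3 says the same; neither makes an exception for early termination. Section 8.3 instead ties recording to the last day of participation: 7 days for non-serious AEs, 30 days for SAEs. It also has unresolved AEs followed up, and has the investigator notify the sponsor of any death or AE "occurring at any time after a subject has discontinued or terminated study participation that may reasonably be related to this study".

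Two places where the conflict might have been settled do not settle it. The text of 5.7.2 covers only withdrawal at the participant's request, although its heading includes termination. Section 7.3.4, on the early termination visit, only refers to the eCRF.

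The embedded trial's primary endpoint is safety from AE reporting (4.2.1). The safety set is everyone given at least one dose (10.3), about 20 patients (5.6, 10.5).

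**The concern.** Read with 5.5 and 8.3, ending participation starts the recording clock early. Two sites, or two investigators, could each follow the protocol and collect different data on the same kind of patient: one monitors to day 30 under 7.3.3, the other stops recording new non-serious AEs 7 days after termination under 8.3.

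For the first ground in 5.7.1, an adverse event is itself the reason for the shortening, so length of follow-up depends on the outcome. The terminated patient stays in the 10.3 denominator while the period in which new events can be counted shrinks. Section 10.4.4 plans summary statistics and mentions no adjustment for time at risk. Late non-serious events would then be under-counted in patients who had already had a problem.

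The second ground offers one further route. Exclusion 7 in 5.2 is "Inability to comply with oral or nasogastric tube administration of study drug", and the risks listed in 2.4.1 include "Gastrointestinal events, including nausea, vomiting, diarrhea, flatulence, abdominal pain". Persistent vomiting could bring a dosed patient within that exclusion.

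**Working it through.** The plan gives no figure to reproduce. The 20 patients are a convenience sample, with no hypothesis test, alpha, power or dropout rate for the interventional trial (10.2, 10.5). The check is arithmetic on the recording windows.

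**Inputs.** Planned safety monitoring: 30 days after last dose (7.3, 7.3.3). Recording after the last day of participation: 7 days for non-serious AEs, 30 days for SAEs (8.3). Let t be the number of days from last dose to termination, t ≥ 0.

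**Formulas.**
- Non-serious AEs are recorded to day t + 7, so the gap in the planned window is max(0, 30 − (t + 7)) = max(0, 23 − t).
- SAEs are recorded to day t + 30, so the gap is max(0, 30 − (t + 30)) = 0 for every t ≥ 0.

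| t (days) | Non-serious AEs recorded to day | Gap in 30-day window | SAEs recorded to day | SAE gap |
|---|---|---|---|---|
| 0 | 7 | 23 | 30 | 0 |
| 7 | 14 | 16 | 37 | 0 |
| 14 | 21 | 9 | 44 | 0 |
| 23 | 30 | 0 | 53 | 0 |

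**Scale across the trial.** The documents do not say how many patients would be terminated this way, so k is an assumption, shown as a range with every termination at t = 0 (the worst case).
- Share of planned 30-day non-serious person-days lost = 23k / (20 × 30).
- For events starting on days 8 to 30, 20 − k patients remain observable. With an assumed 10% risk in that period, the chance of seeing at least one is 1 − 0.9^(20 − k).
- If no such event is seen, the one-sided 95% upper bound on the risk is 1 − 0.05^(1/(20 − k)).

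| k | Person-days lost | Chance of seeing ≥ 1 | Zero-event upper bound |
|---|---|---|---|
| 0 | 0% | 87.8% | 13.9% |
| 2 | 7.7% | 85.0% | 15.3% |
| 4 | 15.3% | 81.5% | 17.1% |
| 6 | 23.0% | 77.1% | 19.3% |

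The last two columns treat the terminated patients as having the same late risk as the others. If their risk is higher, which is the reason for concern under the AE trigger, the true loss of information is larger than shown.

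**The case against.** The strongest reply is that safety capture largely survives termination. This is correct in several respects.

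- A reader might infer that all safety capture is cut short. The documents do not support that: SAE recording reaches day 30 after last dose whatever the date of termination.
- A reader might infer that drug-related problems are the ones most likely to be lost. Section 8.3 points the other way: the triggering event is followed if unresolved, and reasonably related later events are notifiable without time limit. What can drop out is a new non-serious AE, more than 7 days after termination, that nobody judges reasonably related. That safeguard is passive, however, and it rests on a causality judgement that 8.2.2 says should not decide what is reported.
- A reader might treat 5.7.1 as a rule that removes patients. It is permissive, and both grounds carry conditions. The exclusion ground is only weakly tied to outcome. Of the seven exclusions, only number 7 could plausibly follow from a drug effect, and 6.1.6 already allows opened capsules and tube administration.
- Comparing the longest 8.3 window (30 + 7 = 37 days) with 7 days suggests 30 days lost. Measured against the planned 30-day monitoring, the most that can be lost is 23.
- The data deletion in 5.7.2 might seem to apply here. It is written for participant requests only.
- Late liver-test changes are a poor example, because 7.2.1 schedules no study laboratory tests for anyone.
- Section 8.7 says only suspected treatment-related AEs will be reported, so full all-event capture is not certain even for patients who complete follow-up.

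It can also be said that 7.3 and 7.3.3 already require 30 days for everyone. That makes the fault an unresolved conflict rather than a definite cut-off, but it does not tell a site which passage governs. The eCRF may help, but it was not among the documents reviewed, and section 19 places it outside the protocol.

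**Conclusion.** The point holds in a limited form. Sections 5.7.1 and 8.3 together permit a shorter recording period than 7.3 and 7.3.3 require, and nothing in the protocol resolves the difference. The loss is confined to new-onset non-serious AEs. It is max(0, 23 − t) days per affected patient: at most 23 of 30, and none if termination comes 23 or more days after the last dose. The SAE loss within the planned window is zero.

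Under the AE trigger the shortening is informative. With about 20 patients, each one affected is 1/20 = 5% of the safety set. Two to four terminations on the last dosing day would remove 7.7% to 15.3% of planned non-serious person-days. Those shares rest on assumed counts; the 23-day maximum does not. It follows from the documents if sites apply 5.7.1 with 8.3 rather than 7.3.3. The effect is modest, but it falls on the primary endpoint and is easily avoided.

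**What to change.** Reconcile 5.7.1, 7.3.3, 7.3.4 and 8.3 with one common statement. Neither stopping study drug nor termination by the investigator ends safety follow-up. Every patient who received a dose has all AEs, serious and non-serious, collected from the chart to at least 30 days after the last dose, unless the participant withdraws consent. Section 8.3 should give that as a minimum recording period counted from last dose, and 7.3.4 should say that this follow-up continues after an early termination visit.

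Leave the decision on when study drug is stopped as written. No change to 10.3 is needed, since it already keeps every dosed patient in the safety set.

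Within the planned window this restores up to 23 days of non-serious AE recording per affected patient; SAE coverage there is already complete. The cost is a few sentences in an amendment. The follow-up is already planned for all dosed patients and draws on the medical record.

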5.7.2 Handling of Participant Withdrawals or Termination

If a participant requests withdrawal from the study, all data collection will stop and all previously collected data will be deleted from the research database. Any analyses already completed at the time of the withdrawal request will remain unchanged.

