4.2 Study Endpoints

4.2.1 Primary Study Endpoints

Primary Endpoint for Registry Study: Proportion of subjects with decreased left ventricular ejection fraction $\geq 10\%$ from baseline at time of hospitalization

Primary Endpoint for Embedded Clinical Trial: Safety of AT-001 based on adverse events reporting

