10.2 Statistical Hypotheses

The null hypothesis for the registry study is that there are no significant associations between clinical characteristics at study entry and subsequent occurrence of cardiac dysfunction, lung dysfunction or death in hospitalized patients with COVID-19 infection.

There will be no hypothesis testing for the interventional trial. The primary endpoint is safety of AT-001 based on descriptive statistics and qualitative evaluation of adverse event monitoring. Descriptive statistics will be used to assess frequency of secondary endpoints without hypothesis testing.

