10.3 Analysis Datasets

The registry dataset consists of all subjects with any entered data. The interventional safety data set will be all subjects who received at least one dose of AT-001

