13.5 Participant and Data Confidentiality

Information about study subjects will be kept confidential and managed according to the requirements of the Health Insurance Portability and Accountability Act of 1996 (HIPAA). Those regulations require a signed subject authorization informing the subject of the following:

- What protected health information (PHI) will be collected from subjects in this study
- Who will have access to that information and why
- Who will use or disclose that information
- The rights of a research subject to revoke their authorization for use of their PHI.

In the event that a subject revokes authorization to collect or use PHI, the investigator, by regulation, retains the ability to use all information collected prior to the revocation of subject authorization. For subjects that have revoked authorization to collect or use PHI, attempts should be made to obtain permission to collect at least vital status (i.e. that the subject is alive) at the end of their scheduled study period. The research record data will be securely stored on the NYU REDCap database with password controlled access limited to authorized study personnel. The research record will not contain any identifiers. Each subject will be assigned a random study ID number. The link between the subject PHI and the study ID number will be maintained by the PI on encrypted shared drives maintained NYU and in the study binder which is kept in a locked room.

14 Data Handling and Record Keeping

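### Section 5.7.2 erases a withdrawing participant's data even after dosing with AT-001, so the safety analysis cannot cover the set defined in Section 10.3

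*Combined protocol and SAP*

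**What the plan says.** Section 5.7.2 sets one rule for any participant who requests withdrawal: "all data collection will stop and all previously collected data will be deleted from the research database". Its only qualifier is "Any analyses already completed at the time of the withdrawal request will remain unchanged". The rule does not separate registry patients, whose charts are reviewed under a consent waiver, from patients given the investigational drug.

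Section 10.3 defines the analysis set by exposure: "The interventional safety data set will be all subjects who received at least one dose of AT-001". The trial's primary endpoint in Section 4.2.1 is "Safety of AT-001 based on adverse events reporting", and Section 10.2 says it will be assessed by "descriptive statistics and qualitative evaluation of adverse event monitoring", without hypothesis testing. Sections 5.6 and 10.5 put the interventional sample at about 20.

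Two other sections deal with earlier data:

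- Section 5.3, on patients who regain capacity and do not wish to continue: "they will be asked if previously collected data can still be used. If they decline, this data will be discarded".
- Section 13.5, on revoked authorization: the investigator "retains the ability to use all information collected prior to the revocation of subject authorization", and "attempts should be made to obtain permission to collect at least vital status".

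**The concern.** Sections 5.7.2 and 10.3 cannot both be carried out for a dosed patient who withdraws before the analysis. The patient is a member of the safety set by definition, but the database holds nothing to analyse.

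In a 20-patient descriptive study of safety, that is a loss from the primary result. If patients with adverse events withdraw more often, the reported proportions are too low. If event-free patients withdraw more often, they are too high. What disappears is patient-level adverse event data, above all the non-serious events, which are not on the serious event forms. Section 10.1 states that there is no formal SAP, so no later document closes the gap. Section 10.4.5 describes missingness in general terms, but nothing requires erased patients to be counted or shown.

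**Working it through.** **Step 1: the rules side by side for a dosed patient who leaves.**

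| Section | Situation | Earlier data | New data |
|---|---|---|---|
| 5.7.2 | Participant requests withdrawal | Deleted | Stops entirely |
| 5.3 | Capacity regained, declines to continue | Ask first; discard only on refusal | Not stated |
| 13.5 | Authorization revoked | May be used | Seek permission for vital status |
| 7.3, 8.3 | Any dosed patient | All on-study adverse events documented | Safety monitoring to 30 days after last dose |
| 14.2 | Study records generally | Not destroyed without the sponsor's written consent, if applicable | – |
| 10.3 | At least one dose | In the safety set | – |

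None of the other sections is written as an exception to 5.7.2. Staff handling a withdrawal have three different instructions for earlier data: delete, ask, or may use.

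**Step 2: what the deletion does not reach.** It is confined to the research database. Dosing records in EPIC and the pharmacy (6.1.8, 6.2) and serious event forms already sent to the sponsor (8.5) remain. Sponsor notification of possibly related later events (8.3) also continues. The number dosed can therefore still be counted.

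**Step 3: possible size.** The plan states no figure to reproduce. The 20 in Section 10.5 is a convenience sample with no alpha, power or effect size. All event and withdrawal counts below are assumptions. Two-sided intervals are exact (Clopper-Pearson) 95%.

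*Bounds.* With 20 dosed, w deleted and x events among those left, the report shows x/(20 − w). The proportion among all dosed lies between x/20 and (x + w)/20, a width of w/20: 5, 10 and 15 percentage points for w = 1, 2 and 3.

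*One event, and that patient withdraws.* 1/20 = 5.0% (0.1 to 24.9) becomes 0/19 = 0% (0 to 17.6).

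*Four events among 20, two patients withdraw.* The full-set result is 4/20 = 20.0% (5.7 to 43.7). The probabilities in the last column assume withdrawal is unrelated to events: C(4,k) × C(16,2 − k) / C(20,2), with C(20,2) = 190.

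| Event patients among the two (k) | Reported | 95% CI | Bounds over all 20 | Probability |
|---|---|---|---|---|
| 0 | 4/18 = 22.2% | 6.4 to 47.6 | 20% to 30% | 120/190 = 63.2% |
| 1 | 3/18 = 16.7% | 3.6 to 41.4 | 15% to 25% | 64/190 = 33.7% |
| 2 | 2/18 = 11.1% | 1.4 to 34.7 | 10% to 20% | 6/190 = 3.2% |

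The probability-weighted mean is 0.632 × 22.2 + 0.337 × 16.7 + 0.032 × 11.1 ≈ 20%, so unrelated withdrawal causes no bias on average.

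*Precision alone.* After zero events, the one-sided 95% upper bound is 1 − 0.05^(1/n). The chance of seeing at least one event at an assumed true rate of 10% is 1 − 0.9^n.

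| n analysed | Upper bound after zero events | Chance of at least one event |
|---|---|---|
| 20 | 13.9% | 87.8% |
| 19 | 14.6% | 86.5% |
| 17 | 16.2% | 83.3% |
| 15 | 18.1% | 79.4% |

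The loss of precision is modest. Selective loss matters more: three events that all sit in withdrawing patients take 3/20 = 15.0% (3.2 to 37.9) to 0/17 = 0% (0 to 19.5).

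**The case against.** The strongest reply is that the rule seldom bites where it would bias. Deletion follows only a participant's own request. Exits caused by adverse events can run through other routes, such as stopping study drug (Section 2.4.1) or termination by the investigator (Section 5.7.1), and neither expressly deletes data. Patients who die do not request withdrawal. Interventional participation also ends up to 30 days after the last dose (Section 5.5), so the window for a request is short. These points stand, and they limit how many patients could be affected. They do not cover the patient who has an event and asks to leave, which Section 5.7.1 allows at any time.

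A second reply is that Section 10.3 defines membership while 5.7.2 governs data, so an erased patient is still a member with missing data. That is a fair reading, but the analysis still cannot describe the defined set, and the plan does not say how to handle such members.

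Third, Section 13.5 permits use of earlier data without requiring it, so deleting is compatible with that sentence. This is correct. The conflict with 13.5 lies in its attempt to obtain vital status, against a rule that all collection stops. The conflict with 5.3 is plainer: ask first, against automatic deletion.

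Fourth, the main safety information survives. Serious events go to the sponsor within 24 or 72 hours (8.5), data are reviewed daily, and day 7 and day 14 reviews finished before the request arguably stand (8.7). This limits the harm. However, Section 8.7 restricts reporting to suspected treatment-related events, so other non-serious events have their planned home in the database that is erased.

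Finally, erasure protects participants, and the consent form, which was not available here, may have promised it. That limits what can be done for patients already enrolled, and the fix has to respect it.

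**Conclusion.** The concern holds. Section 5.7.2 removes dosed patients' data on request, without exception, and the primary safety summary would then not cover the set in Section 10.3. This follows from the text and does not depend on any assumed rate. It should be fixed.

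The numerical effect is unknown and could be zero, since the documents give no withdrawal or adverse event rate. If 20 are dosed, each deletion widens the range of compatible event proportions by 5 percentage points. Bias arises only if withdrawal is related to events, and it can go either way. The intervals overlap widely and no test is planned, so no formal inference is at risk. The harm is the loss of dosed patients, mainly their non-serious events, from a small descriptive safety set.

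**What to change.** Amend Section 5.7.2 for participants who received AT-001:

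- New collection stops at withdrawal, except for vital status and any adverse event follow-up the participant permits.
- Data collected up to withdrawal are retained and analysed in the Section 10.3 safety set. Dosed patients are also registry patients, so state that this covers their data extracted under the registry procedures too.
- Where the Section 5.3 undertaking to discard refused data is kept, or has already been given, honour it.

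Add to Section 10.3 or 10.4.4 that the report will give the number of dosed participants who withdrew, the number whose data were removed, and best/worst-case bounds on adverse event proportions with all dosed participants as denominator. Reconcile the wording with Sections 5.3, 13.5 and 14.2 and the consent form. The rule for registry-only patients can stay.

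The cost is wording changes and one extra line of reporting, with no extra patients. The downside is that dosed participants may lose automatic erasure of past trial data. The amendment needs IRB approval and, under Section 13.2, a decision on re-consent.
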